2.7.2 Statistical hypothesis, model, and method of analysis

PASI

Summary statistics for PASI 50, PASI 75, PASI 90, PASI 100 response by visit will be presented with absolute and relative frequencies. Confidence intervals for response rates will be derived as well, based on the score method including continuity correction (Newcombe 1998). The summaries will be done using prevalence (observed data), LOCF and NRI approaches.

Summary statistics will be provided for absolute PASI scores and for percent changes from baseline by visit and cohort using prevalence, and LOCF approches. Graphical representations will also be provided on ITT set.

The two cohorts will be compared on PASI scores (absolute change from baseline) using MRMM model with LOCF, prevalence and MI approaches on ITT set.

PASI Changes vs baseline: Linear Mixed Model for Repeated Mesurements (MMRM):

In order to evaluate if there is a differences between cohorts in PASI changes at each time point vs week 0, a longitudinal analyses of changes from baseline will be performed over the course of the study including all the measurements assessed at each time point for the ITT population using a linear mixed model for repeated measurements (MMRM). An unstructured

covariance matrix for the repeated measures within each patient will be applied in the analysis, if the model does not converge, compound symmetry will be used. The explanatory variables in the longitudinal model include cohort, visit, cohort-by-visit interaction, missing data pattern (completers, missing one assessments, missing two assessments, missing three assessments, etc till all visits in the overall study period), propensity score, and corresponding baseline (week 0). The two cohorts will be compared at each time point by reporting a point estimate, p-value, and 95% confidence interval for the treatment difference, based on least squares means.

The propensity score analysis will consider the following baseline factors: age, geographical region (i.e. north vs south vs central), BMI categories (<25 vs >=25), waist circumference, smoking status (Yes vs No), metabolic syndrome (yes vs no), previous PsO therapy (naïve vs previous systemic therapy vs previous biologic therapy), PsA (yes vs no), age at diagnosis of psoriasis, IGA mod 2011 (severe, moderate, mild) as strata factors. This approach allows us also to maximize the analysis model adding only one variable instead of several ones.

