The choice of the MMRM model instead of a simple ANCOVA model on changes vs week 0 considering the prevalence approach or Last observation carried forward (LOCF) approach was done because the LOCF approach would underestimate the within-group mean changes between treatments compared with MMRM, whereas the prevalence approach tend to overestimate the within-group changes (Prakash et al. 2008).

In addition to that, similar MMRM model will be fitted on LOCF and prevalence set without the propensity score approach. An unstructured covariance matrix for the repeated measures within each patient will be applied in the analysis, if the model does not converge, compound symmetry will be used. The explanatory variables in the longitudinal model include cohort, visit, cohort-by-visit interaction, age, geographical region (i.e. north vs south vs central), BMI categories (<25 vs >=25), waist circumference, smoking status, metabolic syndrome (yes vs no), age at diagnosis of psoriasis, and along with interaction terms of each factor with visit.

The SAS codes are described in appendix section.

MMRM with MI approach

MMRM analysis will be also performed using multiple imputation (MI) approach on ITT population.

The multiple imputation will be done with pattern-mixture models (PMMs) as above, that allows formulating assumptions regarding missing data in a transparent and clinically interpretable manner.

The SAS codes are described in appendix section.

PASI 75

A logistic regression analysis model will be also fitted, considering age, geographical region, BMI, smoking status, metabolic syndrome, TNF α -308 polymorphism (if feasible), as well as all clinical relevant variable resulting statistically different at baseline between cohort, as strata factors. The analyses will be done similar to primary analyses based on prevalence, LOCF and NRI approaches using ITT set.

Time to reach PASI 90

The differences between cohorts Cw6-negative and Cw6-positive in time to reach PASI 90 will be evaluated by means of a log-rank test. The hazard ratios and their corresponding 95% confidence intervals will be also computed using a stratified Cox proportional hazards regression model with Cw6 group and baseline PASI as explanatory variable and stratified by geographical region and BMI categories, as well as age categories (tertiles).

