lsmeans sex /ilink cl diff;

run;

proc genmod data=demo_ae ; class cw6 (param = ref ref = "NEGATIVE") sex (param = ref ref = "M") age_group (param = ref ref = "<=40 years"); model numev = cw6 age_group sex / type3 dist=poisson ; estimate "IRR Cw6 (POS vs NEG) " cw6 1 -1; estimate "IRR Age (>40 vs <=40)" age_group 1 -1; estimate "IRR Sex (Female vs Male)" sex 1 -1;

run;

PASI Changes vs baseline: Linear Mixed Model for Repeated Mesurements (MMRM):

The SAS procedure PROC MIXED will be used in the analysis, in particular:

proc mixed data=dataset noclprint;

class cohort vis1n usubjid MissingPattern;

model Changes= cohort week0 dropout visit prop_score

cohort*visit cohort*MissingPattern;

repeated visit/subject=usubjid type=un;

lsmeans cohort*visit/pdiff cl;

run;

where changes includes all changes vs week 0 of PASI; the dropout variable is the missing pattern (i.e. a categorical variable with values of 1, 2, 3 etc.. representing completers, 1 assessment missing, 2 assessments missing, 3 assessment missing etc. in considered dependent variable –e.g. PASI); the prop_score variable is the propensity score. In order to take all the confounding factors into account, the propensity score methodology will be applied and will be included in the final model, as described above. Propensity score will be derived using logistic regression model considering cohort as the dependent variable and baseline covariates as the factors in the model. The derived propensity score will be used as the covariate in the MMRM model.

MMRM with MI approach

Multiple imputation will be performed in SAS using the following three-stage approach:

PROC MI will be applied for each PASI change (or each post baseline PASI score) containing some missing values, which results in creation of multiple copies of this dataset. All copies contain identical values of the non-missing data items, but different values imputed for missing items. The following SAS statement will be used:

proc mi data=PASI_in out=PASI_out seed=1425;

var cohort Baseline PASI score PASI score at week 1 PASI score at week 2 PASI score at week 3 PASI score at week 4 PASI score at week 8 PASI score at week 12 PASI score at week 16 PASI score at week 20 PASI score at week 24;

class cohort;

monotone regression;

run;

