where variables PASI score at week 1 PASI score at week 2 PASI score at week 3... PASI score at week 24 contain missing values for some patients at each PASI time point, which PROC MI will impute using linear regression models.

Then we can calculate changes vs. baseline at each time point

```
data PASI in out1;
```

set PASI_out;

visit="Week 1"; change= PASI score at week 1 – Baseline PASI score; output;

visit="Week 2"; change= PASI score at week 2 - Baseline PASI score; output;...

visit="Week 24"; change= PASI score at week 24 - Baseline PASI score; output; run;

and then we will perform the ANCOVA model using the following statement:

```
proc mixed data= PASI_in_out1;
by visit;
class <As required factors >;
model change =<As per reqired covarites> /;
lsmeans treatment /diff pdiff cl;
ods output diffs=diff_MI lsmeans=LSM_MI;
run;
```

where prop_score is the same continuous variable used for the primary model.

Results of the ANCOVA analysis on 500 imputed dataset will be combined to derive an overall results using the following code:

proc mianalyze parms(classvar=full)=diff_mi;

class cohort;

modeleffects cohort:

ods output parameterestimates=DIFF_MIAN;

by visit;

run;

proc mianalyze data=lsm_mi;

class cohort;

modeleffects cohort:

ods output parameterestimates=LSM_MIAN;

by visit;

run;

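### The SAP describes its multiple imputation of PASI as pattern-mixture with MMRM, but the specified code is MAR regression imputation that ends at week 24 and feeds a by-visit ANCOVA

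*SAP*

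**What the plan says.** SAP 2.7.2, under the heading for MMRM with MI, says "MMRM analysis will be also performed using multiple imputation (MI) approach on ITT population". It then says "The multiple imputation will be done with pattern-mixture models (PMMs) as above" and gives the reason for the choice: it is an approach "that allows formulating assumptions regarding missing data in a transparent and clinically interpretable manner". The only pattern element earlier in that section is an explanatory variable in the MMRM itself: "missing data pattern (completers, missing one assessments, missing two assessments, missing three assessments, etc till all visits in the overall study period".

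SAP 5.4.3 gives the code. The imputation step is introduced with "The following SAS statement will be used". The PROC MI call lists cohort, baseline PASI and PASI at weeks 1 to 24, names cohort as a class variable, and uses "monotone regression". The explanation that follows refers to missing PASI values "which PROC MI will impute using linear regression models". Changes from baseline are then computed up to week 24 and an ANCOVA is fitted by visit. On pooling, the SAP says: "Results of the ANCOVA analysis on 500 imputed dataset will be combined".

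**The concern.** A pattern-mixture imputation needs a stated assumption, by missingness pattern, about how unobserved values differ from what the observed data predict. The text credits the analysis with exactly that. If the code carries no such assumption, a clinical study report that repeats the SAP's description would tell readers that missing-data assumptions had been set out by pattern when none had.

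The code also falls short of the analysis it is meant to implement. A programmer working from it would have to choose how to handle gaps between visits, which visits to include, which model to fit and how to organise the pooling. Those choices would then be made after the data are available.

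**Working it through.** No stated sample size, power or alpha bears on this point, so there is no plan figure to reproduce. The check sets the text beside the code.

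1. **Pattern-mixture claim.** Text (2.7.2): imputation by pattern-mixture models. Code (5.4.3): the imputation variables are cohort, baseline PASI and PASI at each core visit. There is no pattern variable, MNAR statement, shift or reference-based rule, and no pattern-specific assumption is written elsewhere in the SAP. Each missing value is drawn from a regression fitted to patients with that visit observed, given cohort and earlier PASI. That is MAR.

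2. **Where the pattern covariate sits.** In 2.7.2 and 5.4.3 the missing-pattern terms are in the PROC MIXED model for the MMRM. They are not in PROC MI, so they cannot alter an imputed value. The ANCOVA covariates are left as a placeholder; adding a pattern term there would not alter the imputed values either.

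3. **Monotone method.** Monotone regression requires that once a visit is missing, all later visits are missing. SAP 2.5.3 makes provision for missed visits between attended ones, including a rule for a gap flanked by two responses. The coded method does not handle such gaps.

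4. **Visit coverage.** Protocol 6.4.1 and Tables 6-1 and 6-2 schedule post-baseline PASI at weeks 1, 2, 3, 4, 8, 12, 16, 20 and 24 (9 visits) and at weeks 36, 48, 60 and 72 (4 visits): 9 + 4 = 13. The code has the first 9 only, so it covers 9/13 = 69% and omits all 4 extension visits. SAP 2.7.2 sets the PASI change analysis over the whole study, and SAP section 4 extends the analyses to 72 weeks.

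5. **Model fitted.** Text: MMRM. Code: PROC MIXED run separately by visit, described as ANCOVA. SAP 2.7.2 itself gives reasons for choosing MMRM over a simple ANCOVA on LOCF or observed data.

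6. **Number of imputations.** Text: 500. The PROC MI call gives an input dataset, an output dataset and a seed, but no number of imputations, so it would run at the software default.

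7. **Analysis before pooling.** PROC MIANALYZE combines one estimate and standard error per imputed dataset. The PROC MIXED step has a by-statement for visit only, so as printed it does not produce separate results by imputation. It also requests least-squares means for a factor named treatment, where the comparison is by cohort.

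8. **Who has weeks 36 to 72.** Protocol 4.3 admits to the extension only patients who completed the core study, consented again and reached PASI 75 at week 24. About 306 of 406 are expected, so about 406 − 306 = 100 would not enter. Protocol 5.5.12 lets the sponsor end the extension by region after at least 12 weeks. SAP 2.5.3 bars LOCF and NRI imputation for extension patients who completed the study before week 72. Adding the four visits for every patient would therefore impute values for people who were never in the extension.

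**The case against.** **The label has a partial basis.** The words pointing back to the earlier text can refer to the MMRM with its missing-pattern term, which does condition on pattern. This stands as an explanation of where the label came from. It does not make the imputation pattern-mixture.

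**MAR imputation is legitimate here.** Stopping for failure to reach PASI 50 at week 16, or not continuing for lack of PASI 75 at week 24, depends on observed PASI. This also stands. The fault is the disagreement between text and code, not the use of MAR.

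**The code is only a template.** Variable names contain spaces and some model statements are placeholders, so it cannot run as printed, and the missing imputation count and by-statement are probably slips. That is fair for those two items. But other models in the appendix are introduced as sample code, whereas the imputation call is introduced as the statement to be used. The monotone method and the week-24 limit are content, not typing errors.

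Four stronger readings are tempting, and the documents do not support them.

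- A reader might infer that the imputation makes the same assumption as the MMRM, so that agreement between them shows nothing. The main MMRM includes a missing-pattern covariate and the imputation does not, so the assumptions differ. Nor does the SAP present the imputation as a robustness test; 2.7.3 says only that it will also be considered.
- A reader might infer grossly understated standard errors, from analysing the stacked imputations as one dataset. The SAP states that results from 500 datasets are to be combined with PROC MIANALYZE, which requires separate results per imputation.
- A reader might infer that many imputed scores would be negative, because the regression is unbounded and PASI starts at 0. Some could be, but the share depends on the residual spread given cohort, baseline and earlier visits, which the documents do not give. Only imputed values are involved, and they feed mean changes.
- A reader might infer a threat to the primary result. PASI 90 at week 16 is analysed with LOCF, NRI and observed data (SAP 2.5), without this imputation.

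**Conclusion.** The point holds as a defect of specification: the multiple-imputation analysis is wrong as written. What is coded is MAR regression imputation with a by-visit ANCOVA, where the text announces pattern-mixture imputation with an MMRM. It also uses a method unsuited to the gaps the SAP expects, covers 9 of 13 post-baseline visits, and leaves the number of imputations and the by-imputation step out of the code.

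The conclusion rests on reading the two SAP sections together and needs no assumed values. No numerical bias is claimed: the documents give no basis for saying how unobserved PASI differs from what MAR predicts. The consequence is confined to one secondary analysis of change in continuous PASI. It should be corrected before that analysis is run or described.

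**What to change.** - **Name the assumption.** Describe the analysis as multiple imputation under MAR. If the pattern-mixture description is kept, state a pattern-specific departure, such as a delta shift after discontinuation, and code it in the imputation.
- **Handle gaps.** Use fully conditional specification, or MCMC to make the pattern monotone followed by regression.
- **Match the pooling text.** Set `NIMPUTE=500` and add `BY _Imputation_` to the analysis step before PROC MIANALYZE. Name cohort as the compared factor.
- **Reconcile the model.** Fit the stated MMRM within each imputation and pool the cohort differences at each visit, or amend 2.7.2 to say ANCOVA by visit and run it by imputation and visit.
- **Cover the extension.** Add weeks 36, 48, 60 and 72 only for patients who entered the extension. State that the existing rule in 2.5.3, no imputation for those who completed before week 72, applies to this analysis too.

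The cost is a few lines of SAP text and code and a small increase in run time. No new data are needed, and neither the sample size nor the primary analysis changes.

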2.5.2 Statistical hypothesis, model, and method of analysis

The proportion of patients who reach PASI 90 at 16 weeks will be presented with the one-tailed 97.5% confidence interval of the Cw6 positive (POS) – Cw6 negative (NEG) difference.

The null hypothesis:

H0: Cw6 POS - Cw6 NEG \ge 0.12: The difference in proportion of patients achieving PASI 90 response between the Cw6-positive cohort (Cw6 POS) and the Cw6-negative cohort (Cw6 NEG) is at least 12%.

The alternative hypothesis:

HA: Cw6 POS - Cw6 NEG < 0.12: The difference in the proportion of patients achieving PASI 90 response between the Cw6-positive cohort (Cw6 POS) and the Cw6-negative cohort (Cw6 NEG) is less than 12%.

The proportion of PASI 90 response by cohort as well as the difference between cohort together with 97.5% upper CI will be provided using Clopper Pearson CI method.

A logistic regression analysis model will also be fitted, considering age, geographical region (i.e. north vs south vs central), BMI categories (<25 vs >=25), waist circumference, smoking status (Yes vs No), metabolic syndrome (yes vs no), previous PsO therapy (naïve vs previous systemic therapy vs previous biologic therapy), PsA (yes vs no), age at diagnosis of psoriasis, TNF α -308 polymorphism, IGA mod 2011 (severe, moderate, mild) as strata factors.

Model selection:

If model does not converge due to particular covariate(/s), the corresponding covariate(/s) will be removed from the model using Stepwise selection method until model get converged.

Interpretation:

We can conclude that PASI 90 response in the Cw6-negative cohort is not less than 12% with respect to the Cw6-positive cohort if the upper bound of the 97.5 % CI of the difference (Cw6 POS - Cw6 NEG) is less than the non-inferiority margin of 12%.

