2.14 Interim analysis

No interim analysis is planned for this study.

3 Sample size calculation

The primary objective of this study is to evaluate the clinical response in PASI 90 at week 16 of Cw6-negative and Cw6-positive psoriatic patients. According to literature data, Cw6-positive patients will be about 60% of the entire psoriatic patient population.

From a previous study with ustekinumab (Talamonti et al. 2013) we can observe a difference in response to PASI 90 between Cw6-positive vs Cw6-negative patients of around 30%, in favor of Cw6-POS. Therefore, it is sensible to expect a response in the Cw6-negative cohort not less than 12 % respect to the Cw6-positive group. Further considerations are stated in the paragraph below.

Phase III data on secukinumab show a PASI 90 response at 16 weeks of 71%. Under the assumption that 60% of all the enrolled patient population is represented by Cw6-POS patients, we can reasonably assume to observe a proportion of patients with PASI 90 of 80% in the Cw6-POS cohort.

Under these assumptions, considering a one-side alpha level of 0.025 and a power of 80%, 365 patients (219 Cw6-POS and 146 Cw6-NEG) are sufficient to evaluate if the response in terms of PASI 90 in the Cw6-negative cohort is not less than 12% respect to the Cw6-positive cohort.

Considering a dropout rate at 16 weeks of 10% equally divided in the two studied cohorts, a total of 406 patients should be enrolled.

All calculations were done with NQuery 7.0.

A power analysis based on a different Cw6 patient distribution was made in order to facilitate patient enrollment without power-loss in the primary endpoint evaluation. Table 3-1 shows how the enrollment rate should be set free until the ratio between Cw6-POS and Cw6-NEG reaches the 1:1 rate-distribution, with a power of at least 80%.

In particular, the number of Cw6-POS evaluable patients will range from 219 to 182, whereas those in the Cw6-NEG cohort will range from 146 to 182.

Based on the table below, the enrollment in one of the two cohorts will be stopped when the target number is achieved (a maximum of 244 Cw6-POS patients will be allowed).

Table 3-1:Power analysis

Power	Ratio	Cw6	Cw6	Cw6	Cw6	Overall	Cw6	Cw6	

For business use only

		POS	POS	POS	POS		POS	POS
		%	%	Ν	Ν	Ν	%	%
80%	0.66	60%	40%	219	146	365	244	163
80%	0.70	59%	41%	215	150	365	239	167
80%	0.72	58%	42%	212	153	365	236	170
80%	0.75	57%	43%	209	156	365	233	174
81%	0.79	56%	44%	204	161	365	227	179

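### Five covariates of the PASI 90 model enter the PASI 75 logistic model only if a baseline test between cohorts is significant

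*SAP*

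**What the plan says.** The PASI 75 paragraph of SAP 2.7.2 plans an additional logistic regression, "considering age, geographical region, BMI, smoking status, metabolic syndrome", with TNFα-308 polymorphism where feasible. It then opens the list to further variables: "as well as all clinical relevant variable resulting statistically different at baseline between cohort, as strata factors". No significance level is stated, no candidates are listed, and clinical relevance is not defined.

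SAP 2.5.2 gives the PASI 90 model 11 named covariates, with categories such as "previous systemic therapy vs previous biologic therapy" spelled out, and no baseline-significance rule. Its one data-dependent step is stepwise removal of covariates if the model fails to converge. The IGA 0/1 model in SAP 2.7.2 also has a named list.

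Three other places bear on this:
- Protocol 9.5.1 has the cohorts compared on week 16 PASI 75 by the method used for the primary endpoint.
- Protocol 9.2 lets significant baseline variables become covariates.
- SAP 2.3.2 replaces that rule with a table of named variables. SAP Section 4 says that model factors were clarified but does not explain why PASI 75 is treated differently.

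**The concern.** The cohorts are genotype groups, not randomised arms, so the adjusted odds ratio is only as good as its adjustment set. A p-value for baseline imbalance is a poor way to build that set. It takes no account of whether a variable predicts response, and whether it crosses a threshold depends on sample size. A strong predictor with a moderate, non-significant imbalance stays out, while an irrelevant variable with a chance imbalance may come in.

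The rule is also not reproducible as written. SAP 2.3.2 introduces the tested variables as examples, allows a non-parametric substitute where feasible, and gives psoriatic arthritis both a chi-square test and a row in the covariate-adjusted table. Which p-value decides entry is left open. The baseline comparisons use the Safety set, the model the ITT set. Two competent analysts could fit different PASI 75 models to the same data, and a difference between the adjusted PASI 75 and PASI 90 results could come partly from different covariates.

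**Working it through.** **1. The plan's own figure.** Inputs from SAP Section 3 and 2.5.2: one-sided alpha 0.025, power 80%, margin 12 points, "proportion of patients with PASI 90 of 80% in the Cw6-POS cohort". The Cw6-negative rate is not stated; I take it as equal, 80%.

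- n(POS) = (1.960 + 0.842)² × 0.80 × 0.20 × (1 + 219/146) / 0.12² ≈ 218.0, rounded up to 219; n(NEG) = 146. This reproduces "365 patients (219 Cw6-POS and 146 Cw6-NEG) are sufficient".
- SE = √[0.16 × (1/219 + 1/146)] = 0.0427; power = Φ(0.12/0.0427 − 1.960) = 80.2%.
- With 10% dropout, 365/0.90 = 405.6, so 406.

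The covariate rule plays no part in these figures.

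**2. The two lists side by side.**

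| Covariate | PASI 90 (SAP 2.5.2) | PASI 75 (SAP 2.7.2) |
|---|---|---|
| Age, region, BMI, smoking, metabolic syndrome | named | named |
| TNFα-308 | named | named, where feasible |
| Waist, previous psoriasis therapy, psoriatic arthritis, age at diagnosis, IGA | named | only if relevant and statistically different at baseline |

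Six of the 11 are shared; five are conditional.

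**3. Entry by chance.** Assume no true cohort differences, independent tests and a two-sided 0.05 level (the SAP gives none). For the five conditional covariates, P(at least one enters) = 1 − 0.95⁵ = 22.6%. At a 0.10 level it is 1 − 0.90⁵ = 41.0%.

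**4. Real imbalance missed.** With 219 versus 146 patients, the SE of a standardised difference is √(1/219 + 1/146) = 0.107. Power at two-sided 0.05 is Φ(d/0.107 − 1.960):

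| Imbalance | Chance of detection |
|---|---|
| d = 0.1 | 15% |
| d = 0.2 | 46% |
| d = 0.3 | 80% |
| binary factor, 20% vs 25% | 21% |
| binary factor, 20% vs 30% | 59% |

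The binary rows use the usual two-proportion formula (pooled variance under the null, unpooled under the alternative).

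**5. Effect on the cohort estimate.** Simulation, 3,000 runs per setting, 219 versus 146, no true cohort effect, one confounder with log odds ratio 0.5 or 0.8 per SD and standardised difference 0.1 to 0.3, central log odds of response 2.0 (about 88%). All of these are assumptions.

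| Strategy | Mean bias (log odds) | Type I error |
|---|---|---|
| Always adjust | −0.01 to 0.00 | 4.7% to 5.1% |
| Adjust only if test significant | 0.02 to 0.04 | 5.0% to 5.4% |

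The Monte Carlo error on a 5% rate is √(0.05 × 0.95/3,000) = 0.4 points, so the type I error ranges barely differ.

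**6. Can PASI 75 carry the longer list?** The SAP 2.5.2 model has about 15 parameters: cohort 1, age 1, region 2, BMI 1, waist 1, smoking 1, metabolic syndrome 1, previous therapy 2, psoriatic arthritis 1, age at diagnosis 1, TNFα-308 1 (taken as binary), IGA 2. If the week 12 PASI 75 rates for 300 mg in Protocol 1.1 (77.1% and 81.6%) held for 365 patients, non-responders would number 365 × 0.184 = 67 to 365 × 0.229 = 84, or 4.5 to 5.6 per parameter. That is below the 10 events per predictor used in SAP Section 3, if that criterion is applied to the rarer outcome.

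**The case against.** The clause is not a late invention. Protocol 9.2 allowed significant baseline variables into the model, and Protocol 9.4.2 left the primary model open to clinically relevant baseline variables. The PASI 75 sentence keeps that core, adds age, and restricts additions to clinically relevant variables. The model is supplementary to a secondary endpoint. Selection does not look at the outcome, so inflation of type I error is slight. The sentence in SAP 2.7.2 likening PASI 75 to the primary analyses most naturally concerns the missing-data approaches and the ITT set, not the covariates. A shorter list may even suit an endpoint with few non-responders.

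Most of this stands and limits the size of the point. It does not remove it. The SAP closed the list for PASI 90 and IGA 0/1 but not for PASI 75, although Protocol 9.5.1 ties PASI 75 to the primary method. Sparse data are a reason for a short list fixed in advance, not for one settled by baseline p-values.

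A reader might infer more than the documents support:
- *That the whole adjustment set is chosen by significance tests.* Six covariates are named beforehand.
- *That a false selection is likely, for example 1 − 0.95²⁰ = 64%.* No document gives 20 tests or a 5% level for this rule. Several tested variables are already in the model, others are plainly correlated (BMI, weight, waist), and the relevance condition shrinks the pool.
- *That PASI 75 and PASI 90 cannot be compared.* Response rates by visit and the time-to-response analyses share one specification; only the adjusted odds ratios differ.

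**Conclusion.** The point holds as a gap in pre-specification and an unexplained inconsistency between two closely related models, not as a source of large error. Five covariates considered important enough to name for PASI 90 depend on a baseline test for PASI 75, and that test would miss a standardised difference of 0.2 more often than not (about 46% detection at 219 versus 146). Entry of at least one of the five by chance alone has probability about 23%. Bias of 0.02 to 0.04 log odds and type I error of 5.0% to 5.4% are small. These figures rest on an assumed two-sided 0.05 level, independence for the 23%, and a single simulated confounder; several confounders omitted together were not examined. The PASI 90 conclusion, which rests on the confidence interval for the difference, and the sample size of 365 (406 enrolled) do not change.

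**What to change.** In the PASI 75 paragraph of SAP 2.7.2 only:

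1. Delete the provision for variables found statistically different at baseline, and refer instead to the named covariates and categories of SAP 2.5.2. This also removes the feasibility condition on TNFα-308.
2. State that baseline comparisons between cohorts are descriptive and do not determine covariates.
3. State in advance a fixed order in which covariates are dropped if the model is too sparse or does not converge, not based on baseline p-values. Otherwise the stepwise removal in SAP 2.5.2 would bring back a data-driven choice.

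Leave the IGA 0/1 model alone; its list is already named. The cost is a short text edit with no new data, since every covariate is already required for PASI 90. The small downside is sparsity, roughly 67 to 84 non-responders for about 15 parameters under the week 12 rates, and the third step is there to handle it.
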